5.4. Enrollment of Additional Subjects

If there is a subject who cannot be evaluated for DLTs because of withdrawal from the study before the end of Cycle 1 for any reason during the study, additional subjects will be enrolled. In other cases where enrollment of additional subjects is considered necessary, whether or not to enroll additional subjects will be considered through discussion between the investigator and the sponsor. The medical expert may join the discussion as necessary.

5.5. Actions to be Taken for Adverse Events

If a toxicity that falls under the following definition occurs, dose interruption, postponement of the start of the next cycle (hereinafter, postponement), or dose reduction should be performed as shown below.

5.5.1. Occurrence of Dose-limiting Toxicities or Toxicities Equivalent to the Definition of Dose-limiting Toxicities after Cycle 1

If a DLT occurs or a treatment-related toxicity falling under the definition of DLTs occurs after Cycle 1, the investigator or subinvestigator should interrupt, postpone, or discontinue the study treatment. If the toxicity improves to Grade ≤ 1 or the subject recovers to the baseline condition, the investigator or subinvestigator will consider resuming the study treatment at a one-level reduced dose from the dose used in his/her participating cohort (in the case of the 90 mg cohort, resumption at a dose of 90 mg should be considered), only when it is considered beneficial to the subject. Once the dose is reduced, the dose should not be increased again.

The duration of dose interruption must not exceed 4 weeks. If the subject does not recover 4 weeks or more after the onset of the toxicity, the subject should be withdrawn from the study. In case a Grade ≥ 3 toxicity or a serious adverse event (SAE) that is apparently attributable to the primary disease occurs, the study treatment may be interrupted or postponed until the toxicity or the event improves to Grade ≤ 1 or until the subject recovers to the baseline condition.

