5.5.2. Occurrence of the Following Toxicities Not Listed in Section 5.5.1

If any of the following toxicities, not listed in “Section 5.5.1 Occurrence of Dose-limiting Toxicities or Toxicities Equivalent to the Definition of Dose-limiting Toxicities after Cycle 1,” occur, the investigator or subinvestigator will continue the study treatment if the toxicity can be controlled by appropriate intervention.

- Grade ≥ 2 non-hematological toxicity (excluding alopecia) unrelated to the primary disease, Grade ≥ 3 fatigue lasting >48 hours
- Grade ≥ 2 laboratory abnormalities not falling under the definition of DLTs
- Hypoplastic marrow (neutrophil count $<500 /mm^3$ and platelet count $<20,000 /mm^3$)

When it is considered necessary to interrupt or postpone the study treatment, interruption or postponement of the study treatment until the toxicity resolves to the following conditions will be considered. Resumption of the study treatment may be considered if the toxicity is confirmed to have improved or resolved within 4 weeks. When the study treatment is resumed, a reduction to the dose in the cohort that is one-level lower than the dose the pertinent subject was receiving before experiencing the toxicity will be considered.

- Neutrophil count $\geq 500 /mm^3$
- Platelet count $\geq 20,000 /mm^3$
- Grade ≥ 2 non-hematological toxicities (excluding alopecia) that have improved to Grade ≤ 1 or have resolved to baseline levels

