5.6. Withdrawal Criteria

Subjects will be withdrawn from the study for the following reasons.

1. Apparent progression of the disease is found.
2. It becomes difficult to continue the study treatment due to AEs (refer to “Section 5.5 Actions to be Taken for Adverse Events”).
3. A *TP53* mutation is detected after study treatment and it is decided inappropriate to continue the study for the subject.
4. The subject is found to be ineligible for the study after enrollment in the study.
5. The subject withdraws his/her consent to participation in the study.
6. The sponsor decides to prematurely terminate the study.
7. The subject has received the study drug on less than 75% of the specified number of dosing days in Cycle 1.
8. Other cases that the investigator or subinvestigator judges it inappropriate to continue the study for the subject.

If a subject is withdrawn from the study treatment, the investigator or subinvestigator will provide appropriate care to the subject, and record the date and reason of withdrawal in the case report form. The date of withdrawal from the study treatment will not be the date when the event leading to withdrawal occurs, but the date when the investigator or subinvestigator decides on withdrawal.

If a subject is withdrawn due to an AE, the investigator or subinvestigator will provide appropriate treatment to the subject and continue follow-up until resolution or relief of the AE as far as possible.

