11.7.2. Prior Distribution of Bayesian Logistic Regression Model

Assuming that BLRM model parameters $\log(\alpha)$ and $\log(\beta)$ follow bivariate normal distribution, a minimally informative prior distribution is set as follows. If other dosing schedules are assessed, each parameter will be set separately based on the information obtained up to that time.

Parameter	Mean	Standard Deviation	Correlation Coefficient
$\log(\alpha), \log(\beta)$	(-1.8999, 1.3484)	(2.2792, 1.3727)	-0.3157

The above parameters for a prior distribution will be calculated as shown below.

- Based on the overseas Phase 1 study (U102), the median probability of the DLT rate was estimated to be 5% and 20% for the 120 mg qd 21/28 day schedule and the 160 mg qd 21/28 day schedule, respectively.
- From the ratio (0.67) of the dosing days in this study to U102, the median probability of the DLT rate is assumed to be 3% and 13% at doses of 120 mg and 160 mg, respectively, in this study.
- Based on the median probability of the DLT rate at the above doses, parameters of the bivariate normal distribution will be calculated to generate vague prior Bayesian intervals (to minimize prior information) using minimal information beta distribution.

11.7.3. Recommended Dose for the Next Cohort by Bayesian Logistic Regression Model Incorporating the Escalation with Overdose Control Principle

The recommended dose in the next cohort is decided based on posterior distribution of the DLT rate at planned doses (90 mg, 120 mg, and 160 mg). After completing DLT evaluation in 3 subjects per cohort in principle, posterior distribution of the DLT rate at each planned dose will be estimated using BLRM based on the results of DLT evaluation and prior distribution set in “[Section 11.7.2 Prior Distribution of Bayesian Logistic Regression Model](#),” and posterior probability of the DLT rate falling under the following four intervals will then be calculated for each planned dose. The following posterior probabilities can also be calculated for other doses than the planned, as long as the dose is more than 1.3 times but not more than 2 times of the dose in the concerned cohort.

- [0, 16%]: DLT rate interval for under-dosing
- (16, 33%]: target DLT rate interval
- (33, 60%]: DLT rate interval for excessive toxicity
- (60, 100%]: DLT rate interval for unacceptable toxicity

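### After a DLT-level toxicity, Section 5.5.1 names no lower dose for a 160 mg cohort subject already reduced to 120 mg, although 90 mg is a planned level

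*Combined protocol and SAP*

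**What the plan says.** Section 5.5.1 covers a DLT and any treatment-related toxicity that meets the DLT definition after Cycle 1. The investigator first interrupts, postpones or discontinues treatment. If the toxicity settles to Grade 1 or below, or the subject returns to baseline, the investigator considers "resuming the study treatment at a one-level reduced dose from the dose used in his/her participating cohort", and does so "only when it is considered beneficial to the subject". There is one stated exception: "in the case of the 90 mg cohort, resumption at a dose of 90 mg should be considered". The paragraph ends with "Once the dose is reduced, the dose should not be increased again".

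Section 5.5.2 covers listed toxicities that fall outside 5.5.1. If treatment is interrupted and then resumed, the step to consider is "a reduction to the dose in the cohort that is one-level lower than the dose the pertinent subject was receiving before experiencing the toxicity".

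Section 11.7.3 gives the planned doses as 90, 120 and 160 mg. Section 3 sets no limit on the number of treatment cycles.

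**The concern.** The two sections measure the reduction from different starting points. For a first reduction this makes no difference, because the cohort dose and the current dose are the same. They part once a subject has already been reduced.

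Take a 160 mg cohort subject who was stepped down to 120 mg under either section and then has a DLT-level toxicity. One level below the cohort dose is 120 mg, the dose at which the toxicity occurred. The same subject with a lesser toxicity would be considered for 90 mg under 5.5.2. The more serious category thus carries the weaker stated reduction. What is at stake is the safety of that subject if the investigator judges continuation worthwhile: the text offers 120 mg or stopping, and no route to 90 mg.

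**Working it through.** No sample size or error rate bears on this point, and the plan gives no figure to reproduce. The check is to apply both rules to every possible state.

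Inputs:
- Dose levels 90, 120 and 160 mg (Section 11.7.3).
- The 5.5.1 rule: one level below the cohort dose; the 90 mg cohort stays at 90 mg; no increase after a reduction.
- The 5.5.2 rule: one level below the dose being received.

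| Cohort dose | Current dose | 5.5.1 as worded | 5.5.1 with the no-increase sentence | Counted from current dose |
|---|---|---|---|---|
| 160 | 160 | 120 | 120 | 120 |
| 160 | 120 | 120 | **120 (no reduction)** | **90** |
| 160 | 90 | 120 (an increase) | 90 or stop | no lower level |
| 120 | 120 | 90 | 90 | 90 |
| 120 | 90 | 90 | 90 or stop | no lower level |
| 90 | 90 | 90 | 90 or stop | no lower level |

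Reading the table:
- In two states (160 on 160, 120 on 120) 5.5.1 gives a true one-level reduction.
- In three states the subject is already at the lowest level, so no rule could reduce further.
- In one state (160 on 120) a lower planned level exists and 5.5.1 does not name it.

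The no-increase sentence does not repair that state, because going from 120 mg to 120 mg is not an increase. The gap is 120 − 90 = 30 mg/day, or 30/120 = 25% of the current dose.

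Is the state reachable? Section 5.5.1 applies to events after Cycle 1, cycles are not capped, and a first reduction can arise under 5.5.1 or 5.5.2. No section limits a subject to one reduction or requires withdrawal after a second event.

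Could the ladder differ? Section 11.7.3 allows unplanned doses, but Section 5.2.1 requires steps of at least 1.3-fold and Section 5.2.3 gives 160 mg as the planned maximum. From 90 mg, two minimum steps give 90 × 1.3² = 152 mg and three give 90 × 1.3³ = 198 mg. An escalation path therefore has at most three levels.

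Is the MTD analysis affected? Section 11.1 analyses reduced subjects in the dose group before reduction. Section 11.2.2 assigns a subject who resumes at a reduced dose after a DLT to the first dose level received. The resumption dose does not enter.

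**The case against.** The strongest reply is that nobody is made to take 120 mg again. A reader might infer from 5.5.1 that the investigator must re-dose at 120 mg; the text does not support that. Resumption is only considered, after recovery and if beneficial, and discontinuation is open from the start. Failure to recover within 4 weeks means withdrawal. Section 5.6 adds two further grounds: "It becomes difficult to continue the study treatment due to AEs" and "Other cases that the investigator or subinvestigator judges it inappropriate to continue the study for the subject". All of this stands, and it keeps the point minor. It does not supply the missing dose for an investigator who judges that the subject should continue.

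Second, the protocol already accepts resuming at the same dose after a DLT in the 90 mg cohort. True, but no planned level lies below 90 mg. At 120 mg one does.

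Third, 120 mg might be preferred for efficacy. The remissions described in Section 1.3.1 were at 120 and 160 mg, Section 5.2.3 cites a marrow remission at 160 mg on the 14/28 schedule, and none is described at 90 mg. That is an arguable benefit-risk position, but the documents nowhere give it as the reason for the wording. Nor do they state that only one reduction was intended; if it was, the rule should say stop rather than name 120 mg.

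Two other readings go too far. One is that a 160 mg cohort subject already on 90 mg would be raised to 120 mg: the no-increase sentence rules this out, so the wording there is merely awkward. The other is that the harm can be sized from the prior in Section 11.7.2, where "the median probability of the DLT rate is assumed to be 3% and 13% at doses of 120 mg and 160 mg". Those are population values set before any data in this study. They do not describe someone who has just had a DLT-level toxicity at 120 mg. Nor does the time left between this version's date and the planned study end measure how many subjects met the clause.

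**Conclusion.** The point holds as a minor safety correction. In one of six states the only resumption dose that 5.5.1 names is the dose at which the toxicity occurred, 30 mg/day above an available planned level. One in six counts states; it is not a frequency of subjects, and the documents allow no such frequency to be derived. Few subjects can be affected, since the state needs assignment to 160 mg, an earlier reduction, a further DLT-level event, recovery, and a decision to resume.

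Evidence on risk at 120 mg is mixed. DLTs occurred at 120 mg on the 21/28 schedule in the Japanese solid tumor and lymphoma study (Section 1.3.2) and in two subjects of the overseas solid tumor and lymphoma study (Section 1.3.1). The overseas hematology study lists them only at 160 and 210 mg.

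The conclusion assumes that levels means the planned doses and that the cohort wording is applied as written. No estimate or MTD decision changes.

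**What to change.** In Section 5.5.1, count the one-level reduction from the dose the subject was receiving when the toxicity occurred, as 5.5.2 already does. Extend the 90 mg provision from the 90 mg cohort to any subject currently on 90 mg: resume at 90 mg only if beneficial, otherwise discontinue. Keep discontinuation available at every step.

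First reductions stay as they are (160 to 120, 120 to 90, 90 stays at 90). A 160 mg cohort subject on 120 mg would then be considered for 90 mg. No subjects, visits, data or analyses are added. The cost is a protocol amendment under Section 15.8: sponsor assessment, renewed written agreement from investigators, and each center's own procedures. It could reasonably be carried with the next amendment made for other reasons.

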5.5.2. Occurrence of the Following Toxicities Not Listed in Section 5.5.1

If any of the following toxicities, not listed in “Section 5.5.1 Occurrence of Dose-limiting Toxicities or Toxicities Equivalent to the Definition of Dose-limiting Toxicities after Cycle 1,” occur, the investigator or subinvestigator will continue the study treatment if the toxicity can be controlled by appropriate intervention.

- Grade ≥ 2 non-hematological toxicity (excluding alopecia) unrelated to the primary disease, Grade ≥ 3 fatigue lasting >48 hours
- Grade ≥ 2 laboratory abnormalities not falling under the definition of DLTs
- Hypoplastic marrow (neutrophil count $<500 /mm^3$ and platelet count $<20,000 /mm^3$)

When it is considered necessary to interrupt or postpone the study treatment, interruption or postponement of the study treatment until the toxicity resolves to the following conditions will be considered. Resumption of the study treatment may be considered if the toxicity is confirmed to have improved or resolved within 4 weeks. When the study treatment is resumed, a reduction to the dose in the cohort that is one-level lower than the dose the pertinent subject was receiving before experiencing the toxicity will be considered.

- Neutrophil count $\geq 500 /mm^3$
- Platelet count $\geq 20,000 /mm^3$
- Grade ≥ 2 non-hematological toxicities (excluding alopecia) that have improved to Grade ≤ 1 or have resolved to baseline levels

5.6. Withdrawal Criteria

Subjects will be withdrawn from the study for the following reasons.

1. Apparent progression of the disease is found.
2. It becomes difficult to continue the study treatment due to AEs (refer to “Section 5.5 Actions to be Taken for Adverse Events”).
3. A *TP53* mutation is detected after study treatment and it is decided inappropriate to continue the study for the subject.
4. The subject is found to be ineligible for the study after enrollment in the study.
5. The subject withdraws his/her consent to participation in the study.
6. The sponsor decides to prematurely terminate the study.
7. The subject has received the study drug on less than 75% of the specified number of dosing days in Cycle 1.
8. Other cases that the investigator or subinvestigator judges it inappropriate to continue the study for the subject.

If a subject is withdrawn from the study treatment, the investigator or subinvestigator will provide appropriate care to the subject, and record the date and reason of withdrawal in the case report form. The date of withdrawal from the study treatment will not be the date when the event leading to withdrawal occurs, but the date when the investigator or subinvestigator decides on withdrawal.

If a subject is withdrawn due to an AE, the investigator or subinvestigator will provide appropriate treatment to the subject and continue follow-up until resolution or relief of the AE as far as possible.

5.7. Prohibited Concomitant Drugs and Therapies, and Restricted Concomitant Drugs

5.7.1. Prohibited Concomitant Drugs and Therapies

- From informed consent to the day of the Follow-up:
Anticancer treatment other than the study drug (excluding hydroxycarbamide), other investigational products, and investigational medical devices
- From 14 days before the start of study treatment to the day of the Follow-up:
Strong CYP3A inducers and St. John's wort-containing foods and supplements
- From 7 days before the start of study treatment to the day of the Follow-up:
Strong CYP3A inhibitors and grapefruit-containing foods and beverages

Rationale:

These specifications are provided with safety and ethical considerations for patients, and also to eliminate the effects of other drugs on this study as far as possible. Since nonclinical data indicate that DS-3032b is mainly metabolized by CYP3A, these specifications are necessary for the appropriate evaluation of the pharmacokinetics and safety of the study drug.

5.7.2. Restricted Concomitant Drugs

- Hydroxycarbamide should be used as per the following instructions.
Use of hydroxycarbamide is prohibited during the period from 48 hours before treatment with DS-3032b to the start of treatment with DS-3032b. It is, however, allowed to concomitantly use hydroxycarbamide to control white blood cell counts at doses up to 5 g/day for a total of 8 days or less only during the period from after the start of treatment with DS-3032b to the end of the Follow-up.
- Prophylactic treatment for the following symptom is prohibited during the DLT evaluation period. However, treatment given as supportive care for the following symptom is allowed.

- Neutropenia: Granulocyte colony stimulating factor (G-CSF) products etc.

Rationale:

This is set in consideration of the safety of subjects and for the appropriate safety evaluation of DS-3032b.

5.8. Symptomatic Therapy

There are no regulations on symptomatic therapy in this study.

5.9. Management of Subjects

The investigator or subinvestigator will make efforts to maximize the subject's safety throughout the study period. Subjects must be hospitalized during the DLT evaluation period (refer to “Section 5.3.1 Definition of Dose-limiting Toxicities”). The investigator or subinvestigator may allow subjects to temporarily stay out overnight if it is considered feasible after carefully examining the subjects during hospitalization. If a subject stays out overnight, the study center will provide the subject with an instruction beforehand on how to communicate in an emergency.

If an AE occurs during hospitalization and the event is not confirmed to have resolved or be resolving before the scheduled day of hospital discharge, the investigator or subinvestigator will decide whether to continue hospitalization or not, taking the subject's safety into consideration.

6. STUDY PROCEDURES

6.1. List of Study Procedures

Study procedures specified in the protocol are shown in "[Appendix 1](#)."

In the study, the period from the day of informed consent through the end day of the Follow-up is defined as the "study period" for each subject. However, if follow-up of a subject at the study center becomes difficult for such reasons as transfer to another hospital or that the subject refuses to visit the site after the last dose of DS-3032b then the study duration for the pertinent subject will be terminated on the relevant day.

6.2. Study Procedures before Registration of Subjects

The following examinations and assessments, etc. will be performed and the results will be recorded in the case report form.

Data collected before informed consent can also be used if they are obtained within the acceptable limit for each item.

If the study treatment is started on Day 8 or later based on the day of registration defined as Day 0, the patient's eligibility should be assessed again on the preceding day or the start day (before administration) of study treatment.

1. Items confirmed after informed consent obtainment but before the start of subject registration

- Date of informed consent to participate in this study
- Subject identification code
- Date of birth
- Sex
- Race
- Height
- Eligibility
- Medical history and complications

Symptoms that are expressed at the time of informed consent will be recorded as complications.

Regarding medical history, only symptoms/diseases that were cured at the time of informed consent and are considered necessary to be reported at the investigator's or subinvestigator's discretion will be recorded.

- Information on the underlying disease (AML)

Collect data on the date of the first diagnosis, the World Health Organization (WHO) classification, and the date of relapse.

- Prior therapy

The following items will be confirmed:

- Medications for AML: Drug name, stop date, best response, number of courses
- Radiation therapy for AML: Purpose, location, stop date, best response
- Hematopoietic stem cell transplantation: Details, date of transplantation
- Others: Details, stop date
- Assessment of SAEs

Information on SAEs that occur from after informed consent to before the first dose of the study drug will be collected. Information on non-SAEs is not subject to collection during this period.

2. Items performed within 14 days before the day of registration (screening tests)

*Performed on a day as close as possible to the day of registration

- Vital sign measurement

Axillary body temperature, pulse rate, and systolic and diastolic blood pressure will be measured at rest.

- Body weight measurement
- ECOG PS assessment

Subject's general condition will be assessed in accordance with the criteria provided in "[Appendix 2](#)."

- 12-lead ECG measurement (including evaluation of QTcF)

A 12-lead ECG will be performed in the supine position after a 10-minute rest. Each measurement will be performed in triplicate at approximately 1- to 5-minute intervals.

- Laboratory tests

Laboratory Parameters	
Hematology test	Red blood cell count, reticulocyte ratio, hemoglobin, hematocrit, white blood cell count, white blood cell differential count (neutrophils, basophils, eosinophils, lymphocytes, monocytes), platelet count, PT-INR, and aPTT
Blood chemistry test	Total protein, albumin, total bilirubin, direct bilirubin, AST, ALT, ALP, BUN, serum creatinine, uric acid, glucose, electrolytes (K, Na, Cl, Ca, P, Mg), and CRP
Urinalysis	Occult blood, glucose, and protein

- Assessment of bone marrow findings

Assessment will be made based on bone marrow findings and peripheral blood results (neutrophil count, platelet count, and number of blasts) in accordance with “[Section 10.1 Definition of Efficacy Endpoints](#).”

It is desired to obtain bone marrow specimens by bone marrow aspiration and biopsy. If the investigator or subinvestigator considers that the antitumor effect of DS-3032b can be assessed adequately using specimens obtained by bone marrow aspiration only, bone marrow biopsy may be skipped.

- Pregnancy test

A urine or serum pregnancy test will be performed in female subjects.

A pregnancy test is not necessary in women who have been amenorrheic for at least 12 months after the last menstruation and who are considered to have no childbearing potential, or women who are not of childbearing potential after permanent surgical sterilization, etc. In this case, the information and reason will be recorded in the case report form.

A pregnancy test must be performed in women who have been amenorrheic for at least 12 months for medical reasons other than surgical sterilization (eg, medication) because they are considered to have childbearing potential.

3. Items confirmed within 90 days before the day of registration

- HBs antigen, HBs antibody, HBC antibody, HBV-DNA level, HCV antibody, HIV antibody

